9. STUDY ASSESSMENTS

Prior to entry into the study or initiation of any study-related procedures, the subject must read, sign, and date the current Institutional Review Board (IRB)-approved version of the informed consent form. A full discussion of informed consent is presented in Section 13.3.

9.1. Background Characteristics

9.1.1. Medical/Ocular History

If Visit 5a does not occur on the date of Visit 5, the subject should be queried regarding relevant events that may have occurred in the interim.

9.1.2. Concomitant Medications

If Visit 5a does not occur on the date of Visit 5, the subject's concomitant medication list should be updated, if necessary.

9.2. Urine Pregnancy Test

A urine pregnancy test will be performed at each visit for women of childbearing potential only.

9.3. Efficacy Assessments

Efficacy assessments will not be performed in this safety study as the absence of a comparator group and the subject selection process would obviate the possibility of obtaining interpretable efficacy data. Investigators should nevertheless perform any assessments consistent with the standard of care in their practice.

9.4. Safety Assessments

Safety will be assessed at each visit by corrected Snellen VA, slit lamp examination, IOP, AE documentation, and concomitant medication review. Ophthalmoscopy/dilated fundus examination will be performed at the subject's last visit; i.e., Visit 8 (Day 364) or Visit 9 (Day 448).

9.4.1. Corrected Snellen Visual Acuity

Corrected Snellen VA measurement will be performed at each study visit with the Snellen eye chart using the subject's current corrective lens prescription. Subjects must read $\geq 50\%$ of the letters on a single line to accept that VA line. The refraction used at the screening visit of Protocol OTX-101-2016-001 should be used for all subsequent VA assessments for the duration of the study. The subject must wear the same glasses, if applicable, at each visit. If the glasses are not available, the eyeglass prescription should be placed in a trial frame and used in place of the unavailable glasses.

9.4.2. Slit Lamp Examination

A routine slit lamp examination will be performed to evaluate the anterior segment of the eye, including lids, cornea, conjunctiva, anterior chamber, iris, and lens. Abnormalities will be documented.

9.4.3. Intraocular Pressure

Intraocular pressure will be measured via Goldmann applanation tonometry using the clinical site's standard procedures. Intraocular pressure in a given subject should be recorded using the same tonometer and the same observer each time, if possible. The IOP values will be recorded in the eCRF.

9.4.4. Ophthalmoscopy/Dilated Fundus Examination

Direct ophthalmoscopy with dilation will include assessment of the optic nerve head for pallor and cupping. A dilated fundus examination consisting of the vitreous, optic nerve, macula, and peripheral retina will be conducted. Abnormalities will be documented.

9.5. Adverse and Serious Adverse Events

9.5.1. Definition of Adverse Events

An AE is any untoward medical occurrence in a patient or clinical study subject administered a study medication (pharmaceutical/biological product) that does not necessarily have a causal relationship to this medication. An AE can, therefore, be any unfavorable and unintended sign (including abnormal laboratory findings), symptom, or disease temporally associated with the use of the study medication, whether or not related to the study medication. Study medication includes the investigational drug under evaluation and the comparator product or vehicle placebo that is given during any phase of the study.

Medical conditions/diseases present before signing the informed consent form are only considered AEs if they worsen after the informed consent form is signed. Abnormal test results constitute AEs only if they induce clinical signs or symptoms, are considered clinically significant, or require additional therapy or a change in therapy.

At each study visit the subject will be asked how he/she has been feeling. All AEs whether observed by the Investigator or spontaneously reported by the subject will be documented in the subject's chart and the AE eCRF.

Adverse events also may be detected when they are volunteered by the subject between visits or through study assessments.

9.5.1.1. Serious Adverse Event

An SAE is any untoward medical occurrence that at any dose:

- Results in death,
- Is life-threatening,

Note: The term "life-threatening" refers to an event in which the subject was at risk of death at the time of the event; it does not refer to an event which hypothetically might have caused death if it were more severe.

- Results in persistent or significant disability/incapacity (excluding progression/outcome of the disease under study),
- Is a congenital anomaly/birth defect,
- Requires inpatient hospitalization or prolongation of existing hospitalization, or
- Is medically significant; i.e., defined as an event that jeopardizes the health of the subject or may require medical or surgical intervention to prevent one of the outcomes listed above.

Treatment on an outpatient emergency basis that does not result in hospital admission with an overnight stay is not considered an SAE.

All SAEs that are ongoing at the time of completion or discontinuation from the study will be followed until stabilization or resolution of the event.

9.6. Relationship to Study Medication

The relationship of AEs to the study medication should be assessed by the Investigator using the definitions below.

Not suspected: The temporal relationship of the event to the study medication makes a causal relationship unlikely, or, other drugs, therapeutic interventions or underlying conditions provide a sufficient explanation for the observed event.

Suspected: The temporal relationship of the event to the study medication makes a causal relationship possible or other drugs, therapeutic interventions or underlying conditions do not provide a sufficient explanation for the observed event.

If there is any valid reason, even if undetermined, for suspecting a possible cause-and-effect relationship between the study medication and the occurrence of the AE, then the AE should be considered "suspected."

If the relationship between the AE/SAE and the study medication is determined by the Sponsor to be "suspected," the event will be considered to be related to the study medication for the purposes of expedited regulatory reporting.

9.7. Recording Adverse Events

Adverse events spontaneously reported by the subject and/or in response to an open-ended question from the study personnel or revealed by observation, regardless of severity or potential association with the study medication or study procedures, will be recorded in the eCRF. All AEs that occur after a subject has signed the informed consent form until the final study visit should be collected and recorded on the AE eCRF page. Adverse events will be followed until the event is resolved or stabilized, and SAEs that are ongoing at the time of completion or discontinuation from the study will be followed until resolution.

The AE term should be reported in standard medical terminology when possible. For each AE, the Investigator will evaluate and report the following:

- Onset (date);
- Resolution (date);
- Severity grade (mild, moderate, severe);
- Relationship to study medication (not suspected, suspected);
- Action taken (none, study medication temporarily interrupted, study medication permanently discontinued, concomitant medication taken, hospitalization/prolonged hospitalization, other);
- Serious outcome (yes/no).

The severity grade should be determined by the Investigator using the definitions below:

- **Mild:** Discomfort noticed but no disruption of normal daily activity
- **Moderate:** Discomfort sufficient to cause interference with normal daily activity
- **Severe:** Incapacitating, with inability to perform normal activities

It is important to distinguish between serious and severe AEs. Severity is a measure of intensity (as defined directly above) whereas seriousness is defined by the criteria under Section 9.5.1.1. An AE of severe intensity may not be considered serious.

Should a pregnancy occur, it must be reported and recorded on the pregnancy form, as well as in the eCRF. The Sponsor or its designee must also be notified. Pregnancy in itself is not regarded as an AE unless there is a suspicion that the study medication may have interfered with the effectiveness of a contraceptive medication.

The outcome of all pregnancies (spontaneous miscarriage, elective termination, normal birth, or congenital abnormality) must be followed up and documented even if the subject was discontinued from the study.

9.8. Reporting Adverse Events

All SAEs (related and unrelated) will be recorded from the time the subject has signed the informed consent until the final study visit, following the end of treatment exposure. Any SAEs “suspected” to be related to the study medication and discovered by the Investigator at any time after the study should be reported.

Any SAE that occurs must be reported to the Medical Monitor within 24 hours of its occurrence or within 24 hours of learning of its occurrence. Recurrent episodes, complications, or progression of the initial SAE must be reported to the Medical Monitor as follow-up to the original episode within 24 hours of the Investigator receiving the information. Information about all SAEs will be collected and recorded on the SAE form. All pertinent medical records and information collected during the treatment and follow-up of the subject should be maintained at the clinical site with a copy emailed or faxed to the Sponsor or its designee. The Investigator must assess the SAE relationship and complete the SAE form. The Sponsor or its designee may

request additional information. Follow-up information (e.g., discharge summary) will be retained in the subject's chart and a copy will be faxed or emailed to the Sponsor or its designee.

In addition, all SAEs should be recorded on the Adverse Event eCRF page with the serious question marked "Yes."

It is the Investigator's responsibility to notify the approving IRB of any SAEs in accordance with IRB and regulatory requirements.

All subjects who experience an SAE should be followed clinically and undergo the appropriate diagnostic evaluations until stabilization or resolution of the event.

All SAEs will be reported to the US FDA on the appropriate schedule depending if the event is drug related or not drug related, expected or unexpected (based on the available information in the IB).

Any death occurring during the study period should be reported as an SAE and the SAE form must be forwarded to the Medical Monitor within 24 hours of learning of its occurrence. A death that occurs after completion of the study does not require completion of the SAE form.

The Medical Monitor will review and evaluate accumulating safety data from the entire clinical trial database to identify new safety signals or increased frequency of events. This will include a complete review of all SAEs and all follow-up documentation whether relationship to treatment is considered "not suspected" or "suspected".

10. STUDY ACTIVITIES

Error! Reference source not found. provides a tabular summary of all scheduled visits and procedures to be performed during the clinical study.

NOTE: Ophthalmic assessments must be conducted in the order listed in the Schedule of Procedures.

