Exclusion Criteria (continued):

12. Presence of conjunctivochalasis (i.e., mechanical blockage of the lower lid punctum by redundant conjunctiva).
13. Presence of pterygium in either eye.
14. Unwilling to discontinue use of contact lenses during the duration of the study.
15. Preplanned elective surgery or hospitalization during the study period.
16. HIV-positive.
17. Unable to reliably report symptoms and history.
18. Has a severe/serious ocular condition, or any other unstable medical condition that, in the Investigator's opinion, may preclude study treatment or follow-up.
19. Women who are pregnant or breastfeeding.

Investigational Product, Dosage, and Mode of Administration: OTX-101 0.09%, 1 drop in both eyes BID

Reference Therapy, Dosage, and Mode of Administration: N/A

Duration of Treatment: 40 - 52 weeks

Study Procedures: Ophthalmic examinations must be conducted in the order listed in the Schedule of Procedures.

Visit 5a

The site will obtain signed informed consent, inclusion/exclusion criteria, and dispense study medication. If Visit 5a is not conducted on the same day as Visit 5 of Protocol OTX-101-2016-001, the site will also update concomitant medications and conduct a urine pregnancy test for female subjects of childbearing potential.

Visits 6 and 7 (Days 182 and 273)

The site will update concomitant medications, conduct a urine pregnancy test for female subjects of childbearing potential, conduct ophthalmic examinations as specified, document any AEs, and dispense study medication.

Visit 8 (Day 364): Final Treatment Visit for Subjects assigned to OTX-101 0.09% in Study OTX-101-2016-001

The site will update concomitant medications, conduct a urine pregnancy test for female subjects of childbearing potential, conduct ophthalmic examinations as specified and document any AEs. Study medication will be dispensed to those subjects continuing in the study for an additional 12 weeks.

Visit 9 (Day 448): Final Treatment Visit for Subjects assigned to vehicle in Study OTX-101-2016-001

The site will update concomitant medications, conduct a urine pregnancy test for female subjects of childbearing potential, conduct ophthalmic examinations as specified and document any AEs.

Clinical site personnel will document all received and returned study medication at each visit. Study medication accountability will be conducted by the monitor at each applicable monitoring visit.

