If a study subject is discontinued from study medication before Visit 8 or Visit 9, as appropriate, every effort should be made to perform all Visit 8 or Visit 9 procedures during the visit when the subject is discontinued.

Efficacy Assessments: None
Safety Assessments: Safety assessments will include corrected Snellen VA, slit lamp examination, IOP, dilated funduscopy/ophthalmoscopy and collection of AEs and concomitant medications
Criteria for Evaluation: 
• The safety of OTX-101 0.09% as determined by ocular and non ocular AEs
Statistical Methods: Analysis Population: 
• Safety: The safety population will include all patients who have received at least one dose of the study medication. Statistical Analyses: Descriptive statistics will be used to summarize continuous outcomes (number of subjects, mean, standard deviation or standard error of the mean, median, maximum, and minimum) and categorical variables (frequency and percentage) at each assessment time point. All summary tables will be supported with individual subject data listings.

Table 2: Schedule of Procedures

Procedures	Visit 5a	Visit 6	Phone Contact	Visit 7	Phone Contact	Visit 8	Phone Contact	Visit 9	Early Discontinuation
	Day of Study ^a Days since Visit 5a	84 -	182 ± 7 98	227 ± 7 143	273 ± 7 189	318 ± 7 234	364 + 14 ⁱ 280	409 ± 7 325	
Informed consent ^j	X								
Inclusion/exclusion criteria	X								
Concomitant medication history/review	X ^b	X	X	X	X	X	X	X	X
Urine pregnancy test ^c	X ^b	X		X		X		X	X
Corrected Snellen Visual Acuity		X		X		X		X	X
Slit lamp examination		X		X		X		X	X
Ophthalmoscopy/dilated funduscopy						X ^g		X ^g	X
IOP ^d		X		X		X		X	X
Study medication distribution	X	X		X		X ^h			
Adverse event assessment ^e	X	X	X	X	X	X	X	X	X
Study medication accountability ^f		X		X		X		X	X

^a “Day” approximately reflects the cumulative number of days in study (Protocol OTX-101-2016-001 and OTX-101-2016-002), regardless of actual calendar time elapsed. And ‘Day of Study’ is used along with Visit, throughout this protocol – e.g., Visit 6 (Day 182), etc.

^b Performed if Visit 5a is not conducted on the same calendar day as Visit 5 of Protocol OTX-101-2016-001.

^c Women of childbearing potential only.

^d Measure IOP using Goldmann applanation tonometry.

^e Collection of AEs extends from signing of informed consent until the last study visit.

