^f Clinical site personnel will document all received and returned medication at Days 182, 273, 364 and 448. Study medication accountability will be performed by the monitor at each applicable monitoring visit.

^g Examination is required only at the subject’s final visit,

^h Medication is dispensed if the subject is participating for an additional 12 weeks

ⁱ 364 ± 14 days if the subject is participating for an additional 12 weeks

^j Updated ICF due to Amendment #1 to be signed by all participating subjects for Protocol OTX-101-2016-002 Amendment #1

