10.3. Final Study Visit: Visit 8 (Day 364) or Visit 9 (Day 448)

Procedures performed at the subject's final visit; i.e., Day 364 (+14 days) or Day 448 (+14 days), depending on their treatment assignment in Study OTX-101-2016-001, will include the following:

- Collect and document used and unopened study medication materials
- AE assessment
- Concomitant medication review
- Urine pregnancy test (women of childbearing potential only)
- Corrected Snellen VA
- Slit lamp examination
- IOP
- Ophthalmoscopy/dilated fundus examination

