### **7.8. Intraocular Pressure**

Descriptive statistics of the observed and change from baseline IOP will be tabulated for each eye by visit and cohort. Only the results from visits during the extension plus the appropriate baseline visit will be presented. A subject data listing will be provided.

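### The mandatory examination order puts dilated funduscopy before IOP, while the protocol's visit lists put IOP first, so final-visit IOP may be read before or after dilation and the SAP tables cannot tell which

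*Protocol*

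**What the plan says.** The order rule appears twice in the protocol. The Synopsis, under Study Procedures, says "Ophthalmic examinations must be conducted in the order listed in the Schedule of Procedures". The note that opens Section 10 says "Ophthalmic assessments must be conducted in the order listed in the Schedule of Procedures".

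The Schedule is protocol Table 2, reproduced as SAP Table 1. In both copies the eye-examination rows run: Snellen acuity, slit lamp, "Ophthalmoscopy/dilated funduscopy", IOP. Footnote d adds "Measure IOP using Goldmann applanation tonometry". Footnote g says of the funduscopy row "Examination is required only at the subject’s final visit", and the early-discontinuation column is also marked. Dilation is part of that examination: Section 9.4.4 says "Direct ophthalmoscopy with dilation will include assessment of the optic nerve head for pallor and cupping".

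Other places give the reverse order. The Synopsis safety-assessment list, protocol Section 9.4 (repeated in SAP 3.4), and the bullets in Sections 10.3 and 10.5 all name IOP first. In Section 10.3 the last bullet, after IOP, is "Ophthalmoscopy/dilated fundus examination".

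For the analysis, SAP 7.8 says "Descriptive statistics of the observed and change from baseline IOP will be tabulated for each eye by visit and cohort". It does not mention dilation.

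**The concern.** Long-term safety is the only objective, and IOP is one of the few numeric safety measures. The final reading closes the follow-up period. If it is taken under a different condition from the readings at Visits 6 and 7, a change at the last visit could reflect the measurement condition and not the drug, or could hide a drug effect. There is no concurrent control to separate the two.

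The final visit falls at different times in the two cohorts, so a column of the by-cohort table can hold post-dilation readings in one row and mostly undilated readings in the other. If sites differ in which instruction they follow, the mix also varies by site. Protocol Section 9.4.3 asks for the same tonometer and observer each time where possible, so within-subject comparability of IOP is something the plan means to protect.

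**Working it through.** There is no stated figure to reproduce. The check compares passages and then uses simple algebra.

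**1. Which text governs the order?** Only the Synopsis and the Section 10 note claim to set a sequence, and both point to the Schedule. The lists in the Synopsis, 9.4, 10.3 and 10.5 do not say that they set an order. Section 13.7 bars deviation without the Medical Monitor's prior written approval, except in an emergency. Read literally, the Schedule governs. The row order is the same in both documents, so it is unlikely to be an artefact of text extraction.

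**2. Which IOP readings would follow dilation?**

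| Visit | Funduscopy due? | IOP if Schedule order is used | IOP if 10.3/10.5 order is used |
|---|---|---|---|
| 6 and 7 | No | Undilated | Undilated |
| 8, not final | No | Undilated | Undilated |
| 8, final | Yes | After dilation | Before dilation |
| 9 | Yes | After dilation | Before dilation |
| Early discontinuation | Yes | After dilation | Before dilation |

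**3. Who is at the final visit, and when?** Visit 8 is 364 − 84 = 280 days (40 weeks) after Visit 5a. Visit 9 is 448 − 84 = 364 days (52 weeks) after it. By design Visit 8 is final for former OTX-101 subjects and Visit 9 for former vehicle subjects who continue. Protocol Section 6.1 makes the extra 12 weeks an option, Schedule footnotes h and i are worded conditionally, and SAP 5.1 describes the former vehicle cohort as having nine months of active exposure or more. A former vehicle subject who stops at Visit 8 is therefore due for funduscopy there.

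**4. Effect on the Visit 8 means.** Let d be the mean IOP shift caused by dilation, and f the share of former vehicle subjects seen at Visit 8 for whom it is the final visit. Neither is in the documents. If every site follows the Schedule and d is the same in both cohorts:

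- former OTX-101 cohort: artefact = d
- former vehicle cohort: artefact = f × d
- between cohorts: d − f × d = (1 − f) × d

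For illustration only, with d assumed at 0.5, 1 or 2 mmHg:

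| f | d = 0.5 | d = 1 | d = 2 |
|---|---|---|---|
| 0 | 0.5 | 1.0 | 2.0 |
| 0.25 | 0.375 | 0.75 | 1.5 |
| 0.5 | 0.25 | 0.5 | 1.0 |
| 1 | 0 | 0 | 0 |

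If only a share p of final-visit readings follow the Schedule order, equally in both cohorts, each entry is multiplied by p. The documents do not give p either.

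**5. Change from baseline.** No IOP is scheduled at Visit 5a, so under the SAP baseline definition the baseline IOP of both cohorts comes from Study OTX-101-2016-001. The examination order there is not given. Let b be the dilation shift in a cohort's baseline reading (b = 0 if undilated). The artefact in mean change is d − b at a post-dilation final visit and 0 − b at Visits 6 and 7. The difference between them is (d − b) − (−b) = d, whatever b is. The final-versus-earlier contrast within a cohort therefore does not depend on the unknown baseline order. The size of the final change itself does.

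**The case against.** A reader might infer that final-visit IOP is in fact taken after dilating drops in every completer. The documents do not support that. Four protocol lists put IOP first, and a coordinator could reasonably work from the final-visit list in Section 10.3. What is established is a contradiction under which either order may be used.

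A reader might also infer that, at Visit 8, dilation touches one cohort only. That is exact only if f = 0. The extension beyond Visit 8 is optional for former vehicle subjects, and early-discontinuation visits carry the same problem in both cohorts.

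The other side can fairly add three things. First, the Synopsis names adverse events as the criterion for evaluation. IOP is a descriptive table, and no hypothesis test is planned. Second, the Visit 8 cohort contrast is not clean in any case, since at that point the cohorts differ by design in active exposure (about 52 against 40 weeks). Third, if baseline IOP in Study OTX-101-2016-001 was also read after dilation, the final change from baseline would be like for like.

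These points stand, and they lower the weight of the issue. They do not remove it. The lists that put IOP first do not displace a rule stated twice as mandatory. The contrast between Visits 6 and 7 and the final visit survives any baseline order. The planned tables give no means of separating the two kinds of reading.

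**Conclusion.** The plan contradicts itself on the order of a safety measurement, and the order it declares binding makes the measurement condition differ between the final visit and earlier visits. This should be fixed, but no main conclusion of the study turns on it. No sample size, analysis population or test is affected, and readings at Visits 6 and 7 are untouched.

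The size cannot be fixed from the documents. Under full adherence to the Schedule, the artefact in observed Visit 8 means is d in the former OTX-101 cohort and (1 − f)d between cohorts. It vanishes if dilation causes no shift, if sites read IOP first, or, between cohorts, if all former vehicle subjects stop at Visit 8. That dilation may shift a reading is a premise here. The documents name no dilating agent and give neither direction nor size.

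It is tempting to set an assumed shift against a standard error and call it several standard errors. The documents give no standard deviation of IOP change and no count per cohort with a Visit 8 reading, so such a multiple would only restate the assumptions.

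**What to change.** By protocol amendment, move the IOP row above the ophthalmoscopy/dilated funduscopy row in protocol Table 2, and make the same change in SAP Table 1. The mandatory order then agrees with the Synopsis list and Sections 9.4, 10.3 and 10.5, and IOP is read before dilation wherever both are done.

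Some affected visits may already have taken place: the SAP reports 258 subjects enrolled and exposed, and its interim subset at the 12 May 2017 cutoff includes subjects who discontinued early. For completed visits, establish the order where source records show it, and flag post-dilation IOP values in Table 14.3.5 and Listing 16.2.8.2. Where the records do not show it, report the order as unknown.

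The cost is a minor amendment, which Section 13.7 requires to be submitted to FDA and approved by the IRB, plus some site queries and one added data item for past visits. Nothing in the documents shows that the order is captured now, so recovery may be incomplete. No procedure is added for subjects.
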